6. PROCEDURES

* COVID-19 restrictions, if applicable: All interactions for the RCT with research staff will adhere to McMaster University's COVID-19 guidelines as well as government recommendations/protocols. As such, participants will be provided a combination of In Person/Zoom visits. Consent will most often be in person at the hospitals with research staff but if participants from the community choose to review consent over Zoom, they will be asked to sign consents through REDCap during the meeting. Zoom is an externally hosted cloud-based service (https://zoom.us/privacy-and-legal). Participants will be informed of the small risk of a privacy breach for data collected on Zoom. Participants will then be encouraged to express their concerns about using Zoom and be offered the alternative opportunity to participate via phone. An electronic copy of the consent or assent forms will be signed by participants on REDCap.

At the consent visit, regardless of method and site, participants will be fully informed of the protocol for each arm of the study (Usual Care and App group). Participants will also be informed of their chance (50%) of being assigned to either group. Due to the nature of the study participants and researchers are unable to be blinded to their study condition. Once consent is obtained, participants will be randomized to The Usual Care or The App group using computer generated codes. Those in The App group may be given their devices at the ED. Alternatively, if they can't stay for this they can come into The Institute for Applied Health Sciences (IAHS) within 2 days of consent to receive devices and download the App. If a participant is out of reasonable range to visit, devices may be mailed to them via FedEx within 1 day of providing consent and a Zoom meeting arranged to help download The App. If participants do not have an

iPhone above version 6, they will be provided an iPhone and an Apple Watch. They may choose to use their own iPhone if they have one with the appropriate model number. Participants will be informed that all devices supplied must be returned at the end of the study period.

7. INTERVENTIONS

Participants randomized to the control group will be provided Usual Care which often is some type of gradual return guidelines the practice (ED, General Practitioner) subscribes to. These are usually provided in a paper format for the patient to take home. Participants in the Usual Care group will complete symptom surveys every 24 hours via REDCap. The Back2Play App requests symptom surveys be done 3 times daily (quickly done on the watch or phone). The Back2play App also asks users to go to the BrainGames App when participants indicate they are ready to progress to the next stage of RTS in the guidelines. In The BrainGames App they can complete 5 neuropsychological tasks that provide feedback about their readiness to progress. These tasks are not available for those in the Usual Care group.

Surveys about cognitive and physical activities engaged in as well as the participants self-rating of cognitive activity level (1-5) and stage of recovery (1-5/6) are done on a daily basis by both groups.

Participants who have been randomized to the App group will be asked to:

- Download The Back2Play App and The B2P BrainGames App on their iPhone and the Apple Watch provided either at the ED or at a scheduled baseline visit (within 2 days of concussion).
- Pair the Apple Watch to their iPhone and wear an Apple Watch for the duration of the study.
- Complete the initial post-concussion symptom survey on the App with the Research Assistant and receive orientation to The Back2Play App.
- Complete 3 symptom surveys per day on The Back2Play App (Morning, Afternoon and Evening) and daily surveys about cognitive and physical activities as well as self-rating of participants' own cognitive level of activity and stage of concussion recovery until 2 days following symptom resolution.
- Complete games on the B2P BrainGames App (i.e. matching games) which are suggested whenever the participant moves up a stage in RTS Protocol.
- Attend a Zoom Follow Up meeting 2 days after symptom resolution or after a maximum of 3 months of using The App. Here, we will ask participants questions about their perceptions of how well The App guided them through their recovery. Did they agree with classifications and notifications, did they understand the guidelines as well as questions about any other interventions they may have received. This Zoom visit will be recorded and saved to a secure, password encrypted study computer.

- Complete the (SUS) after they have finished using the App (Appendix 1.5). Participate in a Follow Up interview (Appendix 1.6) which will assess the youth's experience with their recovery using The Back2Play App, ask about any other interventions they had and if they have experienced a repeat injury during the time in the study.
- Delete the App from their phone during this interview and arrange to return (by scheduled pick up or FedEx label sent by The Research Assistant) device(s).
- 3 months following study enrollment, participants will be sent a survey through REDCap about reinjury to complete.

Participants who have been randomized to the usual care group will be asked to:

- Receive the usual course of care given by the hospital, General Practitioner or clinic which may or may not include written guidelines, suggestions or resources
- Complete the initial post-concussive symptom survey with The Research Assistant.
- Complete symptom surveys and daily surveys about cognitive and physical activities as well as self-rating of participants' own cognitive level of activity and stage of concussion recovery every 24 hours emailed by REDCap until 2 days following symptom resolution.
- Participate in a Zoom visit 2 days after symptom resolution or after 3 months of
 participation for those who do not achieve symptom resolution. Participants will
 be asked questions regarding their knowledge of and ability to follow the Usual
 Care guidelines they received and about any other interventions they may have
 received. This Zoom visit will be recorded and saved to a secure, password
 encrypted study computer.
- 3 months following study enrollment, participants will be asked to complete a survey about reinjury.

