4. INCLUSION AND EXCLUSION CRITERIA

Inclusion Criteria

Youth aged 10-18 at the time of injury will be included in this proposal. Youth must have had an impact to the head or body and diagnosed with a concussion by a physician. The youth must be symptomatic on admission to the study, and be within the first month of their initial injury. In addition, youth and their parents/guardians must be able to understand and complete questionnaires in English or French.

Exclusion criteria: Youth will be excluded from the study if they 1) have a confirmed significant brain injury requiring resuscitation, 2) were admitted to the pediatric critical care unit or surgical intervention, and 3) if they suffered a concussion but are no longer symptomatic, 4) they have been admitted to the PICU and 5) have been diagnosed with a developmental disability.

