8. DESIGN

Phase 3 of this study has both quantitative and qualitative components. The aims of the qualitative components of the study are to determine if participants liked using The App, and if their experiences of using it helped their recovery from concussion. In addition, qualitative data will be used to review any improvement suggestions to The App before commercialization. Using both qualitative and quantitative research methods we will explore

the usability of The Back2Play App components under consideration for the final version of the App to be commercialized.

Primary Research Outcomes

To assess:

- Risk for repeat head injuries within three months of study completion (3-6 months after injury)
- Duration of symptoms: Time to symptom resolution from date of injury

Secondary Research Outcomes

To assess:

- 1) The frequency of symptoms using PCSS.
- 2) Time to return to activity and time to progress through the 6 stages of RTA
- 3) Perceptions of the platform by parents and youth.
- 4) Accuracy of the algorithm embedded in the background of The App classifying the participant's stage of recovery

Measures

Symptoms

Concussion symptoms will be assessed on The Back2Play App for those randomized to The App group and via REDCap for those randomized to Usual Care. A modified version of the PCSS (consisting of 22 symptoms) will be completed by youth in both groups. The Likert scale was modified to detect the presence of symptoms rather than symptom severity. Symptom data will be collected 3x/day for participants using The Back2Play App and every 24 hours for participants in the Usual Care group.

Cognitive Activity

Cognitive activity will be assessed using a modified version of the scale developed by Brown et al. Participants in both groups will be asked to complete this scale once per day through REDCAP which will appear as follows:

"Please rate 1-5 what you've been doing today"

- 1- None- No reading, homework, text messaging or screen time (T.V., cell phone), can talk on phone
- 2- Minimal- 15 minutes of screen time or schoolwork 2x daily. Socialize with 1-2 friends, no longer than 30 minutes,
- 3- Moderate- Homework in 15 minutes blocks for a maximum of 45 minutes. Screen time/T. V in 15-minute blocks, for up to an hour daily.
- 4- High- Complete as much homework as tolerated. 1 test/week or tests with accommodation (i.e. longer time to write), less reading, homework and screen time than normal
- 5- Full- no restrictions to cognitive activity

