9.5. DATA ANALYSIS PLAN

The recordings of online consent (Zoom), for Phase 3, will be stored on a study computer and saved to a secure password encrypted server. As described above, participants will be asked to complete the (SUS). The SUS yields a single number representing a composite measure of the overall usability of the system being studied. Adjustments and modifications to The Back2Play App will be made before commercializing the product.

We will collect and report descriptively all demographic information, injury-related data (type, mechanism of injury, numbers of injuries), youth premorbid health history. Descriptive statistics such as means, medians, and frequencies will be reported where appropriate. Baseline comparisons will be performed between those that use The App and those whose recovery involved Usual Care with variables of mechanism of injury, age, sex, school performance and concussion history. These variables will be-analyzed using Pearson Chi Squared Cross Tabulations, T-Test and ANCOVA, to ensure the groups are similar. We will also evaluate agreement of the algorithm with the self-reported stage of recovery participants input using these same statistics.

The dichotomous variable, repeat injuries (coded as yes or no), will be analyzed using multivariate logistic regression and resulting odds ratios to determine if using The Back2Play App decreases risk of repeat injury. Confounders of age, gender, number of symptoms, time since last injury and comorbidities of premorbid mental health issues or learning disabilities will be examined as to their potential impact on outcomes. Many of these variables will be correlated with each other and these correlations will need to be examined carefully before they are entered into the analyses.

Time to symptom resolution will be analyzed using survival curves with Multivariate Cox regression analysis. Cox regression (also called proportional hazard models) is a method of survival analysis that models the time until some event as a function of either continuous or categorical predictors, allowing for the fact that not all subjects will experience the events of interest and that they will occur at different times.

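### The App set-up visit is timed from concussion in one section and from consent in another; and curves of symptom duration counted from injury need delayed entry, because only youth still symptomatic up to a month later are enrolled

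*Combined protocol and SAP*

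**What the plan says.** On set-up, section 7 (Interventions) has App-group participants download the App on an iPhone and watch "provided either at the ED or at a scheduled baseline visit (within 2 days of concussion"). Section 6 (Procedures) says that those who cannot stay in the ED can come in "within 2 days of consent to receive devices and download the App", and that for those out of range "devices may be mailed to them via FedEx within 1 day of providing consent".

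On entry, section 4 requires youth to "be within the first month of their initial injury" and adds: "The youth must be symptomatic on admission to the study". It also excludes those whose symptoms have already gone. Section 5 allows randomisation in the ED, but also lets families go home and consent later, and recruits through schools, coaches and clinics.

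On analysis, section 8 lists as a primary outcome "Duration of symptoms: Time to symptom resolution from date of injury". Section 9.5 states: "Time to symptom resolution will be analyzed using survival curves with Multivariate Cox regression analysis", and describes the method as "allowing for the fact that not all subjects will experience the events of interest". That covers censoring. Nothing is said about the days between injury and enrolment. Time since last injury is listed as a potential confounder, but in the paragraph on repeat injury.

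**The concern.** Staff have two deadlines for the same visit. They agree only if consent falls on about the day of injury. A youth who consents on day 3 or later and is set up at a scheduled visit cannot meet section 7. A youth who consents on day 30 could be set up on day 32 under section 6, which is 30 days past the section 7 limit.

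The one-month window also creates left truncation. A youth enrolled on day 20 had to be symptomatic on day 20, so no resolution could have been observed on days 0 to 20. Counting that youth as at risk from day 0 adds to the denominator on days when the event was impossible, and the curve stays too high. The distortion falls on the medians from injury and on the share still symptomatic at one month. One month is the threshold by which the Hypothesis paragraph defines Post-Concussion Syndrome, and readers are likely to set that share beside the 59% cited in section 2.

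**Working it through.** The plan gives no expected median or entry-time distribution, so there is no planned figure to reproduce. Recovery is taken from section 2; entry times are assumed and shown as a range.

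**Inputs.** 59% symptomatic at 1 month and 14% at 3 months (section 2). One month is 30.4 days. The hazard is constant within 0–1 month and within 1–3 months (assumption).

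**True curve.**
- Hazard to 1 month: −ln(0.59)/30.4 = 0.01736 per day.
- Hazard after 1 month: ln(0.59/0.14)/60.8 = 0.02366 per day.
- Median: 30.4 + (ln 2 − 0.5276)/0.02366 = 37.4 days.

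**Curve without delayed entry.** A youth enrolled on day e counts as symptomatic with certainty up to e, then follows the hazard above. With everyone enrolled by day 30:
- Share at one month = 0.59 × average of exp(0.01736e).
- Median = 30.4 + ln(share/0.5)/0.02366.

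Example, entry even over 0–30 days: the average is (exp(0.5207) − 1)/0.5207 = 1.312. The share is 0.59 × 1.312 = 0.774. The median is 30.4 + ln(0.774/0.5)/0.02366 = 48.9 days.

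| Entry pattern among enrolled (assumed) | Share at 1 month (true 0.59) | Median, days (true 37.4) | Excess, days |
|---|---|---|---|
| Even over 0–2 days | 0.600 | 38.1 | 0.7 |
| Even over 0–7 days | 0.627 | 40.0 | 2.6 |
| Even over 0–14 days | 0.668 | 42.6 | 5.2 |
| Half by day 2, half days 2–30 | 0.693 | 44.2 | 6.8 |
| Even over 0–30 days | 0.774 | 48.9 | 11.5 |

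**Second model.** A Weibull fit to the same percentages, with the entry pattern applied to youth approached rather than enrolled, has a true median of 37.8 days. Without delayed entry it gives 38.2 (0–2 days), 43.3 (half by day 2) and 48.1 (0–30 days). With 47% at one month (the hospital clinic figure in section 2) the true median is 27.2 days and the same patterns give 29.0, 36.9 and 45.3. Delayed-entry risk sets returned the true median to within 0.1 day in every case.

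**Treatment comparison.** Simulation with 128 youth (the plan's 160 less 20%), 1:1, 91 days of follow-up after entry, 10,000 runs. Paired values are for entry over 0–30 days and for half by day 2.

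| Cox model | Estimate at true HR 1.6 | Power at HR 1.6 | Power at HR 1.3 |
|---|---|---|---|
| Unadjusted | 1.593 / 1.591 | 0.697 / 0.698 | 0.277 / 0.274 |
| Delayed entry | 1.605 / 1.608 | 0.713 / 0.716 | 0.282 / 0.283 |
| Days from injury as covariate | 1.624 / 1.628 | 0.721 / 0.727 | 0.295 / 0.296 |

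Type I error was 0.046–0.052 throughout.

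**Price in precision.** With 64 controls, the 10th–90th percentile range of the delayed-entry median was 25–48 days (0–30 days) and 30–46 (half by day 2). Without delayed entry it was 42–56 and 38–51. Root mean squared error still favours delayed entry: 9.7 against 12.3 days, and 6.3 against 8.2.

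**The case against.** The trial asks whether the App beats usual care, and that comparison is sound either way. Section 9.5 plans no estimate for all concussed youth and no comparison with the 59%, and section 8 does not list Post-Concussion Syndrome as an outcome. A curve from injury describes the enrolled youth correctly, so a label might be enough. Section 6 expects most consent in person at the hospitals, so entry may be early and the excess small. The set-up conflict is a slip in a task list, and section 6 is workable as it stands.

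Much of this stands. The slip is minor, and if most youth enter within a week the excess is under 3 days on the 59% input. It does not dispose of the point: a primary outcome is defined as duration from injury, survival curves are planned for it, and their medians will be read as durations.

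The correction also has a limit. Delayed entry recovers the true curve only if entry time is independent of recovery time. Concussion clinics and schools may supply late entrants who are slow recoverers. If late-route youth with above-median duration are 2 to 3 times as likely to enrol as faster ones (an assumption), the delayed-entry median is 41–43 days and the unadjusted one 46–48, against a true value of about 37. The bias shrinks but remains.

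Finally, the time-since-injury variable in the repeat-injury paragraph might be meant for the Cox model too. The text is ambiguous, and a covariate would not correct the curves in any case.

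**Conclusion.** Both parts hold. The two set-up deadlines conflict, and section 7 cannot be met by many youth whom section 4 admits. Curves from injury that ignore entry overstate the medians by about 1 to 3 days if entry is within a week and by about 7 to 11.5 days if it spreads to day 30. The one-month share reads 60–63% and 69–77% respectively, against 59%. These sizes rest on the section 2 recovery figures and on assumed entry patterns; the lower 47% input gives a larger excess.

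A reader might infer that the primary treatment test is biased. The documents do not support that: allocation follows enrolment, both arms are truncated in the same way, the hazard ratio moves by about 0.02 or less without adjustment, and type I error holds. Nor should one infer that late entrants are ineligible, since section 4 expressly admits them, or that the correction is free or complete, given the wider spread and the independence assumption. It is a cheap improvement to the reported durations and worth making.

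**What to change.** - **Section 7:** time the baseline visit within 2 days of consent, with the mailing allowance of section 6, and log the date of App activation.
- **Section 9.5:** keep injury as the time origin and use the randomisation date as the delayed-entry time for both the survival curves and the Cox model. Start each curve on the first day with about 10 youth at risk per arm, and label it as conditional on being symptomatic that day. A curve started later than injury should not be set directly against the 59%.
- **State the assumption:** the method takes entry time to be independent of recovery time. If slow recoverers enter later, it reduces the bias but may not remove it.
- **At the least:** name days from injury to randomisation as a fixed covariate in the Cox model. In the simulation this added about 2 to 3 points of power (delayed entry added under 2), but it leaves the curves uncorrected.

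The cost is one phrase, one logged date and a short addition to section 9.5, using dates the trial needs anyway. Eligibility, visits and sample size do not change. The downside is the more variable median shown above.

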3. METHODS

Description of Population and Sample

Our population consists of male and female youth aged 10-18 years that have been diagnosed with a concussion by a physician. Youth presenting to the David Braley Clinic, McMaster Children's Hospital, HWCDSB, Montreal Children's Hospital or physicians in the community will be randomly assigned to the intervention or control groups.

A clinically significant effect of 10% decrease in repeat head injury and 10% decrease in recovery time would be of interest. The sample size calculation was done using parameters with a two sided significance of 0.05 and a power of 0.8 and based on our primary outcome of repeat head injury which is a binomial variable. Our anticipated incidence rate was compared to two rates of incidence in clinical settings and in the literature:

- 16% rate common in the literature
- our anticipated 2% rate with adherence to protocols (from previous B2P study) N=128
- 37% rate from concussion clinic at MCH and
- 13% rate of our pilot data N=100.

The larger number will be sought (sample size takes into consideration 20% refusal rate and loss to follow up) therefore we will recruit N=160. With an average of 25-30 new cases per month from the sources outlined above, 60% consent rate, and 12 months recruitment, it is feasible to attain this sample of youth.

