Appendix 1.6

Follow Up Interview

Ask Everyone:

Tell me about where you are in recovery from your concussion.

Prompts:

Are you still experiencing any symptoms?

Did you hit your head again during your recovery?

If yes did it increase symptoms and how did it affect your recovery?

Are you back fully to school and sport?

Do you feel back to your previous self?

Are there any other therapies or treatments that you tried during your recovery from concussion? Prompts:

Medications, physio, chiro, other medical professionals

Ask App users:

Tell me about your experience in using the App during your recovery from concussion.

Follow Up questions:

Did you receive notifications from the App-give me some examples

Did you do the surveys on your watch or phone?

Did you ever use data or mostly Wi-Fi?

Did you ever forget to charge the watch? How often?

Did you agree with the guidance you were given re: activity or stage levels? (%)

Did you find the App helpful at all in your recovery-how so?

Did you like the App?

Follow up questions:

What were the best features of the App

Were there features you didn't use that much

Were there things that you didn't like or found annoying

How could we make it better?

Ask Usual care group

What was involved in your care and follow up with your concussion?

Were you given some sort of guidelines to follow to return to play and school?

What format were they in?

Did you seek extra treatment or help?

Did you feel you understood how to get better and get back to activities and school after your concussion?

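### Youths who stop the symptom surveys before a symptom-free entry have no backup source for their resolution date, a primary outcome

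*Combined protocol and SAP*

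**What the plan says.** Section 8 (Design) lists time from injury to symptom resolution as one of two primary outcomes. Section 9.5 gives the analysis: "Time to symptom resolution will be analyzed using survival curves with Multivariate Cox regression analysis". It adds that some participants will not have the event, but gives no rule for censoring or for missed surveys.

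The dated symptom record is self-completed. Under Sections 7 and 8 the App arm reports three times a day on the App, and Usual Care reports once every 24 hours through an emailed REDCap link. Both continue until two days after resolution.

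Two later contacts are planned in both arms:

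- **Zoom interview** (Section 7, Appendix 1.6). It takes place two days after resolution. Otherwise it comes after at most three months of App use or, in Usual Care, after three months for youths who have not resolved. All participants are asked an open question about their recovery and "Are you still experiencing any symptoms". No prompt asks for the date symptoms ended.
- **Later survey.** For the App arm Section 7 says "participants will be sent a survey through REDCap about reinjury to complete", three months after enrolment; the Usual Care entry is equivalent. Section 8 (Rate of Reinjury) asks about symptoms only as a consequence of a new blow to the head, and times this contact from symptom resolution instead.

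Section 9.2 says App use stops when symptoms worsen and resumes only after at least 24 hours of rest and resolution of symptoms.

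**The concern.** A youth who feels well may simply stop answering. If that happens before a symptom-free entry is logged, nothing else in the plan asks for the resolution date. The interview set for two days after resolution depends on the same missing entry. In Usual Care the three-month visit is worded for youths who have not resolved, so one who recovered silently fits neither trigger. If the later survey is timed from resolution, as Section 8 has it, that contact has no start date either.

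The analyst is then left with two unsatisfactory choices. Censoring at the last survey makes censoring depend on recovery, which breaks the Cox model's assumption of non-informative censoring. Counting the event at the three-month interview dates it late. Section 6 says researchers are not blinded, so a rule chosen after the data are seen would be hard to defend.

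The affected share could differ by arm, because route, frequency and prompting differ. Read literally, the Section 9.2 pause also interrupts the App arm's only dated source until symptoms have resolved, with no counterpart in Usual Care. That pause and the Section 7 instruction to keep reporting until two days after resolution need to be reconciled.

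**Working it through.** **The plan's own figure.** The only size calculation in Section 3 is "based on our primary outcome of repeat head injury which is a binomial variable", with "two sided significance of 0.05 and a power of 0.8". I used the pooled two-proportion formula without continuity correction:

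n per arm = [1.960·√(2p̄(1−p̄)) + 0.842·√(p₁(1−p₁)+p₂(1−p₂))]² / (p₁−p₂)²

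- 16% v 2%: (0.793 + 0.330)²/0.0196 = 64.4, so 65 per arm and 130 in total (stated 128).
- 37% v 13%: (1.200 + 0.495)²/0.0576 = 49.9, so 50 per arm and 100 in total (stated 100).
- 128/0.80 = 160, as stated.

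These figures reproduce, but they concern re-injury only. The plan gives no figure for time to resolution, so 128 analysed (64 per arm) is used below for scale.

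**Recovery curve.** Section 2 cites 59% symptomatic at one month and 14% at three months. A Weibull curve through both has shape k = ln(ln 0.14/ln 0.59)/ln 3 = 1.197 and a median of about 38 days. Section 3 calls a 10% shorter recovery time of interest. On this curve that is HR = 0.9^(−1.197) = 1.13.

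**Effect of censoring at the last survey.** Let f be the share of recoveries that turn into censoring at about the moment of recovery. The event hazard the model sees is (1−f)·h(t), and the estimated share still symptomatic becomes S(t)^(1−f). The documents give no drop-off rate, so every f is an assumption.

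*Equal shares.* A Cox simulation with 64 per arm, follow-up to day 90 and 4,000 trials per setting left the HR unbiased (0.99 to 1.00 under no effect). Information and the absolute curves suffer:

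| f in both arms | Events: 128 × 0.86 × (1−f) | Estimated symptomatic at 3 months: 0.14^(1−f) | Estimated median | Power at true HR 1.7 |
|---|---|---|---|---|
| 0 | 110 | 14% | 38 days | 81% |
| 20% | 88 | 21% | 45 days | 73% |
| 40% | 66 | 31% | 58 days | 60% |

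Events are under no effect. The median is 37.7 × (1−f)^(−1/1.197).

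*Unequal shares, no true effect.* HR ≈ (1−f_App)/(1−f_UC):

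| f App | f Usual Care | Formula | Simulated HR |
|---|---|---|---|
| 5% | 20% | 0.95/0.80 = 1.19 | 1.18 |
| 20% | 5% | 0.80/0.95 = 0.84 | 0.85 |
| 10% | 20% | 0.90/0.80 = 1.125 | 1.12 |
| 10% | 30% | 0.90/0.70 = 1.29 | 1.28 |
| 30% | 10% | 0.70/0.90 = 0.78 | 0.78 |

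The first three rows used 40,000 per arm. The last two used 64 per arm, where the 5% test rejected in about 20% of trials.

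**Effect of dating the event at the interview.** Section 4 admits youths up to one month after injury, so a three-month visit can fall about three to four months after injury. A youth who recovered on day 20 would be recorded at about day 90 or later.

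**The case against.** The strongest objection is that the documents contain no censoring rule. A reader might infer that the plan censors a youth who goes quiet on recovery, and that the hazard ratio will therefore be biased. The text does not support that. Such a youth could be censored at the last survey, counted as an event at the interview, or treated as interval-censored, and the plan chooses none of these. What stands is that it provides neither a rule nor a date to apply one to.

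Four further objections narrow the point:

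- The three-month interview is a partial fallback. It collects current symptom status, and the open question might draw out a date. Nothing requires that date to be recorded, and the Usual Care wording leaves silent recoverers outside the visit.
- A youth who logs one symptom-free entry before stopping already has a date and is unaffected.
- The later survey form is not in the documents, so its content is known only from its description.
- The shares are assumed, and equal shares leave the hazard ratio unbiased. The 20% in Section 3 combines refusal with loss to follow-up and does not measure stopping on recovery. Differential loss is a possibility the design leaves open, not a finding.

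The Section 9.2 pause could also mean resolution of the worsening only, which would make the interruption shorter. Phase 3 is also labelled a feasibility RCT, which lowers the stakes somewhat, but resolution time is still a primary outcome.

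**Conclusion.** The point holds for youths who stop before any symptom-free entry: the plan has no backup source for their resolution date and no rule for handling its absence. Later analysis cannot supply a date that nobody asked for.

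The size depends on an unknown. Under last-survey censoring, an equal 20% share costs about 22 of 110 events and raises apparent three-month persistence from 14% to about 21%, without biasing the hazard ratio. A 15-point difference between arms (5% v 20%) moves a null hazard ratio to 1.19 or 0.84, a shift at least as large as the effect of interest (about 1.13). These results assume the Weibull curve from Section 2, follow-up from injury to day 90 and the stated shares. They illustrate a mechanism and do not estimate this trial's bias, whose direction is unknown. The change is worth making because it is cheap.

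**What to change.** 1. Add one item to the part of the Appendix 1.6 guide asked of all participants, and to the later REDCap survey: is the youth free of concussion symptoms and, if so, on what date did they end? Put it to every randomised youth in both arms, including those who stopped the daily surveys.
2. State the rule in Section 9.5. Where no symptom-free survey entry exists, the recalled date is the event date, bounded below by the last symptomatic report and above by the first symptom-free contact.
3. Pre-specify two sensitivity analyses: resolution interval-censored between those two contacts, and censoring at the last survey. The first needs an interval-censored model instead of the standard Cox fit.
4. Reconcile the timing of the later survey (Section 7: three months after enrolment; Section 8: three months after symptom resolution), and reconcile the Section 9.2 pause with the Section 7 reporting schedule.

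The cost is one question on two existing contacts and a short addition to the analysis plan. Recalled dates are less exact than daily reports, and some youths who ignored the surveys will also miss the later one. The question does not define symptom resolution, which the plan also leaves without an operational definition; the same definition should govern the surveys and the new item.
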